11.1.3 Other Safety Findings

Other Safety Findings (regardless of association with an adverse) include:

- Medication errors, overdose, whether accidental or intentional, misuse, or abuse, involving an Amgen product,
- Pregnancy and lactation exposure,
- Transmission of infectious agents,
- Reports of uses outside the terms for authorized use of the product including off-label use,
- Occupational exposure,
- Any lack or loss of intended effect of the product(s).

11.1.4 Product Complaints

Product Complaints include any written, electronic or oral communication that alleges deficiencies related to the identity, quality, durability, reliability, safety, effectiveness, or performance of a product or device after it is released for distribution to market or clinic by either Amgen or by distributors and partners for whom Amgen manufactures the material. This includes any drug(s) or device(s) provisioned and/or repackaged /modified by Amgen. Drug(s) or device(s) includes investigational product.

Product complaints of Blincyto will be reported.

11.2 Safety Reporting Requirements

CCI is responsible for ensuring that safety events (adverse events, product complaints and other safety findings) reported by the physician, patient/caregiver or interviewer that occur in patients treated with Blincyto after study enrolment through the final study contact and submitted as individual case safety reports to Amgen via the applicable Amgen Safety Reporting Form (paper form) within 1 business day of awareness.

See [Appendix C](#) for sample Safety Report Form(s), [Appendix D](#) for Additional Safety Reporting Information regarding the adverse event grading scale used in this study, and [Appendix E](#) for sample Pregnancy and Lactation Notification Worksheets.

The physician may be asked to provide additional information for any event submitted, which may include a discharge summary or extracts from the medical record. Information provided about the event must be consistent with the medical records.

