Haemato-oncologists/nurses in participating centres will include patients and their associated caregivers who fulfil all the selection criteria listed below in a consecutive manner according to the date of initiation of treatment with Blincyto until reaching the target number of patients/caregivers to be recruited per centre. Caregivers can be a spouse, family member, friend or professional helper who has helped with Blincyto treatment. The consecutive selection of patients and caregivers at each site is designed to minimise selection bias and to allow for the study results to be generalisable to the entire population of Blincyto treated patients. To assess generalizability of the data, sites will be asked to keep a log of anonymized demographic profiles (age and sex) of patients administered Blincyto, and their caregivers.

CCI

[figure not shown]
Figure 1. Illustration of sampling strategy

Patients/caregivers who agree to participate in the study with informed consent will be asked to complete a paper questionnaire after discharge from hospital **preferably** when they return to clinic for a bag change or monitoring (Figure 2). Both the patient and the caregiver will be invited to participate in the survey: **however, one can participate without the participation of the other**. If the patient is not well enough to complete the questionnaire on returning to clinic after hospital discharge on Blincyto, the patient will be asked again at the next visit. If a caregiver is not available at a visit, they will be asked at the next available visit to participate. Only one caregiver per patient will be recruited.

Appropriate measures will be adopted to ensure physicians do not influence patient/caregiver's choices (e.g. patients and caregivers will place their completed questionnaires in a sealed envelope).

Figure 2. Illustration of treatment characteristics and questionnaire administration

Note: Patients/Caregivers will complete the questionnaire based upon their first exposure to Blincyto at home. However, the questionnaire may be administered subsequent to blincyto cycle 1

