9.2.3.2 Exclusion Criteria

- Patient and/or caregiver of a patient who has only received Blincyto as an in-patient **only**.
- Patient/caregiver is currently employed by Amgen/delegate.
- **Patient and/or caregiver of a patient who is participating in Blincyto clinical trials or is receiving Blincyto through a compassionate use program**

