9.2.4 Baseline Period

This is a cross-sectional survey that does not involve any follow-up of patients and caregivers. Eligibility criteria will be assessed and patient/caregiver questionnaire completed at one point in time within the data collection period.

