9.7.2.3.1 Description of Study Enrollment

The study populations as identified in the recruitment process will be described. Recruitment rates and a description of the number of patients/caregivers in the study and analysis populations will be provided.

Analysis sets: As shown in [Figure 3](#), datasets for analysis will be further described in the SAP and will include:

- Study population: All adult patients with R/R Ph- B-precursor ALL initiating Blincyto (or their caregivers).
- Eligible Set: All patients/caregivers who fulfill the eligibility criteria.
- Enrolled Set: All eligible patients/caregivers who agree to participate in the study.
- Full Analysis Set: All patients/caregivers who complete the questionnaire of their corresponding survey and have valid responses to allow for the assessment of the primary objective.
- Safety Set: This is the same as the Enrolled Set.

Figure 3. Study Population and Datasets flow-chart

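### Read literally, the safety reporting window in section 11.2 leaves out events from earlier home use that come to light at the survey contact

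*Protocol*

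**What the plan says.** Section 11.2 of the protocol covers adverse events, product complaints and other safety findings. It limits them to those "that occur in patients treated with Blincyto after study enrolment through the final study contact", and asks for submission to the sponsor within 1 business day of awareness. Section 11.1.3 counts as other safety findings "Medication errors, overdose, whether accidental or intentional, misuse, or abuse, involving an Amgen product".

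The design is described differently. Section 9.2.4 states: "This is a cross-sectional survey that does not involve any follow-up of patients and caregivers". It continues: "Eligibility criteria will be assessed and patient/caregiver questionnaire completed at one point in time within the data collection period". Enrolment is defined in section 9.7.2.3.1: "Enrolled Set: All eligible patients/caregivers who agree to participate in the study". The same list adds: "Safety Set: This is the same as the Enrolled Set".

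Section 9.2.3.1 requires that the patient has already had Blincyto as an outpatient. Section 9.2.3.2 correspondingly excludes any "Patient and/or caregiver of a patient who has only received Blincyto as an in-patient". The note to Figure 2 in section 9.2.2 says that respondents "will complete the questionnaire based upon their first exposure to Blincyto at home". Section 9.9 explains that the questionnaire is placed after discharge partly so that any medication errors have had time to happen.

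**The concern.** A window from enrolment to last contact suits a study that follows people forward in time. This survey looks back. By the time someone can be enrolled, the home use that the materials are meant to make safer has already begun.

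Suppose a respondent mentions a pump error from the previous week, or an answer points to one when CRO staff open the envelope. Applied literally, section 11.2 does not require that event to be sent on through the study, because it occurred before enrolment. Medication errors and neurological events are the two risks for which the educational materials were introduced (section 7.1). What is at stake is the capture of individual safety reports in a post-authorisation safety study. The survey estimates are not at stake.

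**Working it through.** The plan gives no figure to reproduce. The check sets the order of events against the window and measures the time on each side.

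**Order of events**
1. The patient receives Blincyto as an outpatient, which eligibility requires (sections 9.2.3.1 and 9.2.3.2).
2. The eligible person agrees to take part, which is enrolment (section 9.7.2.3.1). The window in section 11.2 opens here.
3. The questionnaire is completed. Section 9.2.4 puts eligibility assessment and completion at one point in time, and no follow-up comes after. The protocol does not define the final study contact separately, so the window closes here.

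Step 1 always starts before step 2, so the home exposure that makes someone eligible always begins outside the window.

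**Length of the window**
- Consent and questionnaire at the same visit: about 0 to 1 day.
- Consent at one visit and completion at a later one, because the patient was unwell or the caregiver absent (section 9.2.2): the gap between those visits. This case is an assumption, since the protocol does not say whether consent is taken at the first approach.

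**Home infusion that can precede enrolment in cycle 1**
- Inputs from section 7.1: a cycle is 4 weeks, or 28 days, of infusion, and the minimum recommended hospital stay is 9 days.
- Home days available = 28 − 9 = 19.
- This is a maximum. Completion is preferably at a return visit for a bag change or monitoring, and the brochure in Appendix F gives bag changes every 1 to 4 days. A respondent surveyed at the first bag change might have had only 1 to 4 days at home.

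Home time before enrolment is thus anything from a few days to 19 days in cycle 1, against a window of about 0 to 1 day in the same-visit case.

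**Who would see an event first**
Questionnaires go into a sealed envelope (section 9.2.2), are entered by CRO staff (section 9.6.1), and no queries are planned (section 9.6.3). The CRO may be the first to see a response that suggests an error, and the duty set out for it is the one in section 11.2.

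**The case against.** Several points on the other side are sound.

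*Asked about events.* A reader might infer that respondents are asked whether a medication error or neurological event happened to them. The documents do not show that. Sections 9.3 and 9.3.2 list receipt, knowledge, behaviours, usage and understanding. The questionnaire is a stand-alone document (Appendix A) that is not shown. Section 11 expects very few reports because the format is multiple choice. Events may still come to light in conversation with site staff, or be suggested by a behaviour answer, but that is an inference.

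*Drafting.* The sentence in section 11.2 is broken: its closing part about submission lacks a verb. The period may have been meant for when events are reported. As written, however, it is attached to when they occur, and the 1-business-day clock only sets the speed of submission. An ambiguity that allows a literal reading to drop reports still needs repair.

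*Other routes.* Section 11.2.1 keeps the sponsor's general pharmacovigilance duties, section 11.1.4 has product complaints reported without naming a window, and the brochure tells patients to call the doctor or nurse at once and gives a side-effect reporting route. So not all reporting is lost. None of these passages tells site or CRO staff to forward an adverse event or medication error that began before enrolment.

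*Larger exposure.* A reader might count the whole course of up to five cycles as excluded time. That span would include treatment-free intervals and hospital days, and it does not fit the instruction to answer from the first home exposure.

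*Interpretation.* A reader might also infer that the survey can no longer be read alongside safety outcomes, as section 7.2 intends. Section 7.2 does not say that those outcomes come from case reports in this survey, so the inference is unsupported.

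**Conclusion.** The point holds as a defect in the study-specific reporting rule. On its literal wording, section 11.2 sets a nearly empty window in a one-contact survey. It leaves out events from earlier home use, up to 19 days in cycle 1, even when they become known at the survey contact or at data entry. This conflicts with section 11.1.3, which makes medication errors reportable, and with section 9.9, which times the survey so that they can have occurred.

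The conclusion rests on three assumptions: the period applies to occurrence, consent and completion usually share a visit, and discharge follows the minimum stay. If consent comes earlier, the window grows only by the gap between visits. If the hospital stay is longer or completion earlier, fewer home days are excluded, but those before enrolment still fall outside.

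The number of reports affected cannot be estimated from the protocol and is probably small. No primary or secondary endpoint changes. The correction is still worth making, because it is cheap and concerns safety capture.

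**What to change.** Rewrite the sentence in section 11.2 so that it is grammatical and turns on awareness. For example: the CRO ensures that any adverse event, product complaint or other safety finding in a patient treated with Blincyto, of which site or CRO staff become aware from enrolment through the final study contact and data entry, is submitted to the sponsor within 1 business day of awareness, whatever its onset date.

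Optionally, the data management plan could list the questionnaire responses to be flagged at data entry as possible medication errors. Whether this is useful depends on the questionnaire, which is not shown, and the plan may already provide for it.

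The cost is one sentence in the protocol, a matching line in site and data-entry instructions, and possibly a few more individual case reports. Sample size and analysis are unchanged.

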11.2.1 Safety Reporting Requirement to Regulatory Bodies

Amgen will report safety data as required to regulatory authorities, Investigators/institutions, IRBs/IECs or other relevant ethical review board(s) in accordance with Pharmacovigilance guidelines and in compliance with local regulations. The Investigator is to notify the appropriate IRB/IEC or other relevant ethical review board of Serious Adverse Events in accordance with local procedures and statutes.

12. Administrative and Legal Obligations

12.1 Protocol Amendments and Study Termination

Amgen may amend the protocol at any time. If Amgen amends the protocol, written agreement from the Investigator must be obtained where applicable per local governing law and/or regulations. The IEC or other relevant ethical review board in the participating countries must be informed of all amendments and give approval. The Investigator **must**

send a copy of the approval letter from the IEC or other relevant ethical review board in the participating countries to Amgen.

Amgen reserves the right to terminate the study at any time. Both Amgen and the Investigator reserve the right to terminate the Investigator's participation in the study according to the contractual agreement. The Investigator is to notify the IEC or other relevant ethical review board in the participating countries in writing of the study's completion or early termination and send a copy of the notification to Amgen.

13. Plans for Disseminating and Communicating Study Results

The protocol, study status updates and report(s) will be included in regulatory communications according to the risk minimisation plan, periodic benefit-risk evaluation reports and other regulatory milestones and requirements.

This study will be registered on the European Network of Centres for Pharmacoepidemiology and Pharmacovigilance (ENCePP) website before the start of data collection, and the study summary results will be posted on this public website no later than 12 months after study termination (defined as 'database lock').

A final study report will be developed and submitted to PRAC, and will serve as a basis for the development of publications and presentations in scientific journals, and press releases.

Abstracts, summaries, presentations and manuscripts will be prepared in line with dissemination guidelines of the International Committee of Medical Journal Editors (International Committee of Medical Journal Editors n.d.) and Guidelines for Good Pharmacoepidemiology Practice (International Society for Pharmacoepidemiology 2008) to help ensure the quality and integrity of pharmacoepidemiological research and to provide adequate documentation of research methods and results.

13.1 Publication Policy

The results of this study will be submitted for publication. Authorship of any publications resulting from this study will be determined on the basis of the International Committee of Medical Journal Editors (ICJME) Recommendations for the Conduct, Reporting, Editing and Publication of Scholarly Work in Medical Journals, which states:

- Authorship credit should be based on (1) substantial contributions to conception and design, acquisition of data, or analysis and interpretation of data; (2) drafting the article or revising it critically for important intellectual content; (3) final approval of the version to be published and (4) agreement to be accountable for all aspects of the work in ensuring that questions related to the accuracy or integrity of any part of the work are

appropriately investigated and resolved. Authors should meet conditions 1, 2, and 3 and 4.

- When a large, multicenter group has conducted the work, the group should identify the individuals who accept direct responsibility for the manuscript. These individuals should fully meet the criteria for authorship defined above.
- Acquisition of funding, collection of data, or general supervision of the research group, alone, does not justify authorship.
- All persons designated as authors should qualify for authorship, and all those who qualify should be listed.
- Each author should have participated sufficiently in the work to take public responsibility for appropriate portions of the content.

All publications (e.g., manuscripts, abstracts, oral/slide presentations, book chapters) based on this study must be submitted to Amgen for corporate review. The vendor agreement will detail the procedures for, and timing of, Amgen's review of publications.

14. Compensation

Patients/caregivers will not receive any incentives for their participation in the survey. Investigators will receive a compensation for the recruitment of participants into the study if permitted under applicable regional laws or regulatory guidelines. This compensation will be based on a Fair Market Value (FMV) assessment (e.g., time and effort) in each participating country.

15. References

- Benjamin, J.E. & Stein, A.S., 2016. The role of blinatumomab in patients with relapsed/refractory acute lymphoblastic leukemia. *Therapeutic Advances in Hematology*, 7(3), pp.142–156.

Appendix A. List of Stand-alone Documents

No.	Title
1	Patient/Caregiver Questionnaire

Appendix B. ENCePP Checklist for Study Protocols

EUROPEAN MEDICINES AGENCY
 SCIENCE MEDICINES HEALTH

European Network of Centres for
 Pharmacoepidemiology and
 Pharmacovigilance

Doc.Ref. EMA/S40136/2009

ENCePP Checklist for Study Protocols (Revision 3)

Adopted by the ENCePP Steering Group on 01/07/2016

The [European Network of Centres for Pharmacoepidemiology and Pharmacovigilance \(ENCePP\)](#) welcomes innovative designs and new methods of research. This Checklist has been developed by ENCePP to stimulate consideration of important principles when designing and writing a pharmacoepidemiological or pharmacovigilance study protocol. The Checklist is intended to promote the quality of such studies, not their uniformity. The user is also referred to the [ENCePP Guide on Methodological Standards in Pharmacoepidemiology](#), which reviews and gives direct electronic access to guidance for research in pharmacoepidemiology and pharmacovigilance.

For each question of the Checklist, the Investigator should indicate whether or not it has been addressed in the study protocol. If the answer is "Yes", the section number of the protocol where this issue has been discussed should be specified. It is possible that some questions do not apply to a particular study (for example, in the case of an innovative study design). In this case, the answer 'N/A' (Not Applicable) can be checked and the "Comments" field included for each section should be used to explain why. The "Comments" field can also be used to elaborate on a "No" answer.

This Checklist should be included as an Annex by marketing authorisation holders when submitting the protocol of a non-interventional post-authorisation safety study (PASS) to a regulatory authority (see the [Guidance on the format and content of the protocol of non-interventional post-authorisation safety studies](#)). The Checklist is a supporting document and does not replace the format of the protocol for PASS as recommended in the Guidance and Module VII of the Good pharmacovigilance practices (GVP).

Study title: A cross-sectional survey of patients and caregivers receiving Blincyto in routine clinical practice in Europe to evaluate the effectiveness of additional risk minimisation measures

Study reference number:

Section 1: Milestones	Yes	No	N/A	Section Number
1.1 Does the protocol specify timelines for				
1.1.1 Start of data collection ¹				6
1.1.2 End of data collection ²				6
1.1.3 Study progress report(s)				
1.1.4 Interim progress report(s)				
1.1.5 Registration in the EU PAS register				6
1.1.6 Final report of study results				6

¹ Date from which information on the first study is first recorded in the study dataset or, in the case of secondary use of data, the date from which data extraction starts.

² Date from which the analytical dataset is completely available.

ENCePP Checklist for Study Protocols (Revision 3)

Comments:

This is a cross-sectional study and thus neither study progress reports nor interim progress reports are expected to be developed during the study conduct.

Section 2: Research question	Yes	No	N/A	Section Number
2.1 Does the formulation of the research question and objectives clearly explain:				
2.1.1 Why the study is conducted? (e.g. to address an important public health concern, a risk identified in the risk management plan, an emerging safety issue)				4, 7
2.1.2 The objective(s) of the study?				4, 8
2.1.3 The target population? (i.e. population or subgroup to whom the study results are intended to be generalised)				4, 9.2
2.1.4 Which hypothesis(-es) is (are) to be tested?				
2.1.5 If applicable, that there is no a priori hypothesis?				

Comments:

This study is descriptive and therefore no formal hypothesis will be tested.

Section 3: Study design	Yes	No	N/A	Section Number
3.1 Is the study design described? (e.g. cohort, case-control, cross-sectional, new or alternative design)				4, 9.1
3.2 Does the protocol specify whether the study is based on primary, secondary or combined data collection?				4, 9.1
3.3 Does the protocol specify measures of occurrence? (e.g. incidence rate, absolute risk)				
3.4 Does the protocol specify measure(s) of association? (e.g. relative risk, odds ratio, excess risk, incidence rate ratio, hazard ratio, number needed to harm (NNH) per year)				
3.5 Does the protocol describe the approach for the collection and reporting of adverse events/adverse reactions? (e.g. adverse events that will not be collected in case of primary data collection)				11

Comments:

Section 4: Source and study populations	Yes	No	N/A	Section Number
4.1 Is the source population described?				9.2
4.2 Is the planned study population defined in terms of:				
4.2.1 Study time period?				4, 9.2.1
4.2.2 Age and sex?				4, 9.2.3
4.2.3 Country of origin?				4, 9.1, 9.2

ENCePP Checklist for Study Protocols (Revision 3)

Section 4: Source and study populations		Yes	No	N/A	Section Number
4.2.4	Disease/indication?				4, 9.2.3
4.2.5	Duration of follow-up?				
4.3	Does the protocol define how the study population will be sampled from the source population? (e.g. event or inclusion/exclusion criteria)				4, 9.2.2

Comments:

This is a cross-sectional design with no follow-up.

Section 5: Exposure definition and measurement		Yes	No	N/A	Section Number
5.1	Does the protocol describe how the study exposure is defined and measured? (e.g. operational details for defining and categorising exposure, measurement of dose and duration of drug exposure)				
5.2	Does the protocol address the validity of the exposure measurement? (e.g. precision, accuracy, use of validation sub-study)				
5.3	Is exposure classified according to time windows? (e.g. current user, former user, non-use)				
5.4	Is exposure classified based on biological mechanism of action and taking into account the pharmacokinetics and pharmacodynamics of the drug?				

Comments:

No exposure-outcome association will be assessed

Section 6: Outcome definition and measurement		Yes	No	N/A	Section Number
6.1	Does the protocol specify the primary and secondary (if applicable) outcome(s) to be investigated?				4, 9.3
6.2	Does the protocol describe how the outcomes are defined and measured?				4, 9.3
6.3	Does the protocol address the validity of outcome measurement? (e.g. precision, accuracy, sensitivity, specificity, positive predictive value, prospective or retrospective ascertainment, use of validation sub-study)				4, 9.3
6.4	Does the protocol describe specific endpoints relevant for Health Technology Assessment? (e.g. HRQoL, QALYs, DALYs, health care services utilisation, burden of disease, disease management)				

Comments:

This is a cross-sectional survey with no HEOR objectives

Section 7: Bias		Yes	No	N/A	Section Number
7.1	Does the protocol describe how confounding will be addressed in the study?				

ENCePP Checklist for Study Protocols (Revision 3)

Section 7: Bias	Yes	No	N/A	Section Number
7.1.1. Does the protocol address confounding by indication if applicable?				
7.2 Does the protocol address:				9.9
7.2.1. Selection biases (e.g. healthy user bias)				9.9
7.2.2. Information biases (e.g. misclassification of exposure and endpoints, time-related bias)				9.9
7.3 Does the protocol address the validity of the study covariates?				

Comments:

No strenght of association between exposure and outcome is measured

Section 8: Effect modification	Yes	No	N/A	Section Number
8.1 Does the protocol address effect modifiers? (e.g. collection of data on known effect modifiers, sub-group analyses, anticipated direction of effect)				9.7

Comments:

Section 9: Data sources	Yes	No	N/A	Section Number
9.1 Does the protocol describe the data source(s) used in the study for the ascertainment of:				
9.1.1 Exposure? (e.g. pharmacy dispensing, general practice prescribing, claims data, self-report, face-to-face interview)				9.4
9.1.2 Outcomes? (e.g. clinical records, laboratory markers or values, claims data, self-report, patient interview including scales and questionnaires, vital statistics)				9.4
9.1.3 Covariates?				9.4
9.2 Does the protocol describe the information available from the data source(s) on:				
9.2.1 Exposure? (e.g. date of dispensing, drug quantity, dose, number of days of supply prescription, daily dosage, prescriber)				9.4
9.2.2 Outcomes? (e.g. date of occurrence, multiple event, severity measures related to event)				9.4
9.2.3 Covariates? (e.g. age, sex, clinical and drug use history, co-morbidity, co-medications, lifestyle)				9.4
9.3 Is a coding system described for:				
9.3.1 Exposure? (e.g. WHO Drug Dictionary, Anatomical Therapeutic Chemical (ATC) Classification System)				
9.3.2 Outcomes? (e.g. International Classification of Diseases (ICD)-10, Medical Dictionary for Regulatory Activities (MedDRA))				
9.3.3 Covariates?				
9.4 Is a linkage method between data sources described? (e.g. based on a unique identifier or other)				9.6.2

ENCiPP Checklist for Study Protocols (Revision 3)

Comments:

--

Section 10: Analysis plan	Yes	No	N/A	Section Number
10.1 Is the choice of statistical techniques described?				4, 9.7
10.2 Are descriptive analyses included?				4, 9.7
10.3 Are stratified analyses included?				4, 9.7
10.4 Does the plan describe methods for adjusting for confounding?				
10.5 Does the plan describe methods for handling missing data?				9.7.2.2
10.6 Is sample size and/or statistical power estimated?				4, 9.5

Comments:

--

Section 11: Data management and quality control	Yes	No	N/A	Section Number
11.1 Does the protocol provide information on data storage? (e.g. software and IT environment, database maintenance and anti-fraud protection, archiving)				9.6
11.2 Are methods of quality assurance described?				9.8
11.3 Is there a system in place for independent review of study results?				13

Comments:

The Final Report will be sent to PRAC for approval.

Section 12: Limitations	Yes	No	N/A	Section Number
12.1 Does the protocol discuss the impact on the study results of:				
12.1.1 Selection bias?				9.9
12.1.2 Information bias?				9.9
12.1.3 Residual/unmeasured confounding? (e.g. anticipated direction and magnitude of such biases, validation sub-study, use of validation and external data, analytical methods)				
12.2 Does the protocol discuss study feasibility? (e.g. study size, anticipated exposure, duration of follow-up in a cohort study, patient recruitment)				9.2.2, 9.9

Comments:

--

Section 13: Ethical issues	Yes	No	N/A	Section Number
13.1 Have requirements of Ethics Committee/ Institutional Review Board been described?				10

ENCePP Checklist for Study Protocols (Revision 3)

Section 13: Ethical issues	Yes	No	N/A	Section Number
13.2 Has any outcome of an ethical review procedure been addressed?				10
13.3 Have data protection requirements been described?				10

Comments:

Section 14: Amendments and deviations	Yes	No	N/A	Section Number
14.1 Does the protocol include a section to document amendments and deviations?				5

Comments:

Section 15: Plans for communication of study results	Yes	No	N/A	Section Number
15.1 Are plans described for communicating study results (e.g. to regulatory authorities)?				13
15.2 Are plans described for disseminating study results externally, including publication?				13

Comments:

Name of the main author of the protocol:

PPD

